8.1.1 Eligibility screening

Following registering in the IRT for screening, participant eligibility will be checked once all screening procedures are completed. The eligibility check will be embedded in the IRT system. Please refer and comply with detailed guidelines in the IRT manual.

8.1.2 Information to be collected on screening failures

Participants who sign an informed consent form and subsequently found to be ineligible will be considered a screen failure. The reason for screen failure should be entered on the applicable Case Report Form. The demographic information, informed consent, and Inclusion/Exclusion pages must also be completed for screen failure participants. No other data will be entered into the clinical database for participants who are screen failures, unless the participant experienced a serious adverse event during the screening phase (see SAE section for reporting details).

Participants who sign an informed consent and are considered eligible but fail to be started on treatment for any reason will be considered an early terminator. The reason for early termination should be captured on the appropriate disposition Case Report Form. Data and samples collected from participants prior to screen failures may still be analyzed (i.e. specifically, mutation test for *BRAF* from either Central or Local Lab collected from participants prior to screen failure.)

8.2 Participant demographics/other baseline characteristics

The data to be collected on participant characteristics at screening includes:

- Demography (age, gender, childbearing potential, race and ethnicity, or as allowed by local regulations)
- Past and current medical conditions including cardiovascular medical history and risk factors
- Diagnosis and extent of cancer using AJCC edition 8
- Alcohol history
- Smoking history
- HIV history
- Prior antineoplastic therapies (medications, radiation, surgeries)
- Prior and current concomitant medications, surgical and medical procedures and significant non-drug therapies. Note: All other medications taken within 28 days or 5 half-lives, whichever is shorter before the first dose of study treatment is administered must be recorded on the Prior and current concomitant medication eCRF page and updated on an ongoing basis if there is new change to the medication.

Assessments to be performed at screening/baseline include:

- Physical examination (e.g. performance status (ECOG), height, weight, vital signs, ophthalmic and skin examination)

- Cardiovascular assessments (e.g., ECG, ECHO or MUGA)
- Laboratory assessments (e.g., hematology, chemistry, thyroid function, coagulation, urinalysis, serum pregnancy test)
- Tumor assessment (RECIST 1.1, color digital photography including metric ruler for skin lesions, etc.)

8.3 Efficacy

8.3.1 Efficacy assessments

Tumor response will be assessed locally and by independent central review according to the Novartis guideline version 3.2 ([Section 16](#)) based on RECIST 1.1 ([Eisenhauer et al 2009](#)). The imaging assessment collection plan is presented in [Table 8-2](#). Details of the central review process will be described in the independent review charter.

Imaging data will be centrally collected and checked for quality by an imaging Contract Research Organization (CRO) designated by Novartis. The central independent review's assessment will be used for the primary endpoint analysis and local investigator's assessment will be used for treatment decision making.

Information regarding prior interventions (e.g., radiotherapy), pre-existing radiographic findings that mimic metastatic disease at baseline/screening and prior interventions should be transmitted to the imaging CRO via the Baseline Clinical Form along with the baseline images. Sites must ensure the data entered on the form is consistent with the data entered in the clinical database.

Information regarding cytology/histology results should be transmitted to the imaging CRO via the cytology and histology report form for all visits, when applicable, for review by the independent radiologist. Sites must ensure the data entered on the form is consistent with the data entered in the clinical database.

Baseline imaging assessments

Imaging assessments will be performed at screening/baseline within 28 days of start of treatment (Day -28 to Day -1 prior to Day 1).

Any imaging assessments already completed during the regular work-up of the participant within 28 days prior to start of treatment, including before signing the main study ICF, can be considered as the baseline images for this study. Any imaging assessments obtained after enrollment cannot be considered baseline images. The following assessments are required at screening/baseline:

- Chest, abdomen, and pelvis CT or MRI
- Brain CT or MRI
- Whole body bone scan
- Localized bone CT, MRI, or x-ray, for any lesions identified on the whole body bone scan that are not visible on the chest, abdomen, and pelvis CT or MRI
- Color photography including a metric ruler to measure the size of the lesion for any skin lesions present

- CT or MRI of other metastatic sites (e.g. neck), if clinically indicated

If a participant is known to have a contraindication to CT intravenous (IV) contrast media or develops a contraindication during the trial, a non-contrast CT of the chest (MRI is not recommended due to respiratory artifacts; however, if CT is not feasible per local regulations, MRI can be performed instead) plus a contrast-enhanced MRI (if possible) of the abdomen and pelvis should be performed.

A brain MRI or CT should be completed for all participants to identify brain metastases. Contrast enhanced brain MRI is preferred, however, if MRI contrast is contraindicated, then MRI without contrast or CT with/without contrast is acceptable.

A whole body bone scan should be performed per institutional standard of care [e.g. Tc-99 bone scan, whole body bone MRI, Fluorodeoxyglucose positron emission tomography (FDG-PET), or sodium fluoride (NaF) PET]. Localized CT, MRI, or X-rays should be acquired for all skeletal lesions identified on the screening whole body bone scan, which are not visible on the chest, abdomen, and pelvis CT/MRI.

If clinically indicated, CT or MRI of other areas (e.g. neck) of disease as appropriate should be performed.

If skin lesions are present at screening, color photography should be acquired using a digital camera in clear focus, including a scale/ruler, in such a way that the size of the lesion(s) can be determined from the photograph.

Any potentially measurable lesion that has been previously treated with radiotherapy should be considered as a non-measurable lesion. However, if a lesion previously treated with radiotherapy has clearly progressed since the radiotherapy, it can be considered as a measurable lesion.

[figure not shown]
Chest x-rays and ultrasound should not be used to measure tumor lesions.

Post-baseline imaging assessments

Imaging assessments as described in [Table 8-2](#) should be performed using the same imaging modality used at baseline, irrespective of study treatment interruption or actual dosing (see [Table 8-1](#)). Imaging assessments for response evaluation will be performed every 6 weeks (+/- 7 days) for the first 36 weeks, and every 12 weeks (+/- 7 days) thereafter until disease progression, death, lost to follow-up or withdrawal of consent. Imaging assessments should be scheduled using the enrollment date as the reference date (not the date of the previous tumor assessment), and should be respected regardless of whether treatment with study treatment is temporarily withheld or unscheduled assessments performed.

Additional imaging assessments may be performed at any time during the study at the investigator's discretion to support the efficacy evaluations for a participant, as necessary. Clinical suspicion of disease progression at any time requires a physical examination and imaging assessments to be performed promptly rather than waiting for the next scheduled imaging assessment.

Each lesion that is measured at baseline must be measured by the same method (either same imaging method or by photography, including a metric ruler) and when possible, the same local

radiologist/physician throughout the study so that the comparison is consistent. If an off-schedule imaging assessment is performed because progression is suspected, subsequent imaging assessments should be performed in accordance with the original imaging schedule.

Combined PET/CT may be used only if the CT is of similar diagnostic quality as a CT performed without PET, including the utilization of IV contrast media. At the discretion of the Investigators, FDG-PET scans may be performed to document progressive disease per RECIST 1.1 ([Appendix 1](#)).

Table 8-2 Imaging Assessment Collection Plan

Procedure	Screening/Baseline	During Treatment/Follow-up
Chest, abdomen and pelvis CT or MRI (with intravenous contrast enhancement)	Mandated	Mandated, every 6 weeks (+/- 7 days) until Week 36, and every 12 weeks (+/- 7 days) thereafter
Brain CT or MRI	Mandated	If lesions were documented at baseline, follow same schedule as CT/MRI of chest, abdomen, and pelvis, or if clinically indicated
Whole body bone scan	Mandated	If clinically indicated
Localized bone CT, MRI, or x-ray	For any lesions identified on the whole body bone scan that are not visible on the chest, abdomen and pelvis CT or MRI	If lesions were documented at baseline, follow same schedule as CT/MRI of chest, abdomen, and pelvis, or if clinically indicated
Color photography (with scale/ruler)	For any skin lesions present	If lesions were documented at baseline, follow same schedule as CT/MRI of chest, abdomen, and pelvis, or if clinically indicated
CT or MRI of other metastatic sites (e.g. neck)	If clinically indicated	If lesions were documented at baseline, follow same schedule as CT/MRI of chest, abdomen, and pelvis, or if clinically indicated
During a Public Health emergency as declared by Local or Regional authorities i.e., pandemic, epidemic, or natural disaster, that limits or prevents on-site study visits, the collection of images may be modified by Novartis and will be communicated to the investigator		

8.3.2 Transmission of radiological data to central independent review

All radiological assessments will be read locally and should be submitted promptly after acquisition to the imaging vendor designated by Novartis. Rapid image transmission to the central imaging vendor will be accomplished by transferring the images acquired by the investigator electronically in a secured website (e.g.: via the internet).

All imaging timepoints will be read on an ongoing basis as detailed in the imaging manual to be provided by the designated imaging vendor and independent review charter. In all instances, the process at the imaging vendor will ensure that the central reviewers remain blinded to the results of the local assessment. Results of these readings will not be communicated to the sites.

In case patients continue treatment beyond disease progression as outlined in [Section 6.1.4.1](#), images should still be sent to the imaging vendor.

8.4 Safety

Safety assessments are specified below with the assessment schedule detailing when each assessment is to be performed.

For details on AE collection and reporting, refer to AE section.

As per [Section 4.6](#), during a Public Health emergency as declared by Local or Regional authorities i.e., pandemic, epidemic or natural disaster, that limits or prevents on-site study visits, regular phone or virtual calls can occur for safety monitoring and discussion of the participant's health status until it is safe for the participant to visit the site again.

Table 8-3 Physical Examination, Vital Signs, Height and Weight & Specifications

Assessment	Specification
Physical examination	
A complete physical examination will be performed at screening and later as clinically indicated and will include the examination of general appearance, skin, neck (including thyroid), eyes, ears, nose, throat, lungs, heart, abdomen, back, lymph nodes, extremities, vascular, and neurological. If indicated based on medical history and/or symptoms, rectal, external genitalia, breast, and pelvic exams will be performed.
 
A short physical exam will include the examination of general appearance and vital signs (blood pressure [SBP and DBP] and pulse). A short physical exam will be performed at all visits starting from visit 3 as per schedule in Table 8-1 except where a complete physical examination is required.
 
Information for all physical examinations must be included in the source documentation at the study site. Clinically relevant findings that are present prior to signing informed consent must be recorded on the appropriate CRF that captures medical history. Significant findings made after signing informed consent which meet the definition of an Adverse Event must be recorded as an adverse event.

Vital signs	Vital signs include blood pressure (supine position preferred when ECG is collected), pulse measurement, and body temperature. Vital signs will be measured at screening and at subsequent time points as specified in Table 8-1
Height and weight	Height in centimeters (cm) will be measured at screening. Body weight (to the nearest 0.1 kilogram (kg) in indoor clothing, but without shoes) will be measured at screening and at subsequent time points as specified in Table 8-1 .
Dermatological Examination/Skin Biopsy/Photography	A full body dermatological examination will be performed by a dermatologist (or suitably qualified medical personnel) to identify abnormal skin lesions. All findings will be photographed and identified during screening. Dermatological examinations should include examination of skin and assessment of any skin changes. Dermatological examinations will be obtained at each time point as noted in the Assessment Schedule (Table 8-1). Wherever possible, the same individual should perform these examinations. Biopsy in or around skin lesions that change during the study may be obtained if clinically indicated. Skin photography and de-identified pathology reports of new lesions or lesions that change during the study must be obtained and forwarded to Novartis or designee.

ECOG Performance status:

Performance status will be assessed as described in the [Table 8-1](#). More frequent examinations may be performed at the investigator's discretion, if medically indicated. ECOG Performance status scale will be used as described in [Table 8-4](#):

Table 8-4 ECOG performance status scale

Score	Performance Status
0	Fully active, able to carry on all pre-disease performance without restriction
1	Restricted in physically strenuous activity but ambulatory and able to carry out work of a light or sedentary nature, e.g., light housework, office work
2	Ambulatory and capable of all self-care but unable to carry out any work activities. Up and about more than 50% of waking hours
3	Capable of only limited self-care, confined to bed or chair more than 50% of waking hours
4	Completely disabled. Cannot carry on any self-care. Totally confined to bed or chair
5	Dead

8.4.1 Laboratory evaluations

Local laboratory will be used for analysis of scheduled hematology, biochemistry, and other blood specimens collected as part of safety monitoring (as detailed in [Table 8-5](#)). The frequency of the assessments is indicated in the [Table 8-1](#).

For assessment of participants' eligibility to the study, laboratory results from local laboratory will be used.

The results of the local laboratory will be recorded in the eCRF.

The CRA will obtain the local laboratory reference ranges and a copy of the laboratory certification for all laboratory results that are entered into the eCRF.

As per [Section 4.6](#), during a Public Health emergency as declared by Local or Regional authorities i.e., pandemic, epidemic or natural disaster, that limits or prevents on-site study visits, if participants cannot visit the site for protocol specified safety lab assessments, an alternative lab collection site may be used.

Table 8-5 Clinical laboratory parameters collection plan

Test Category	Test Name
Hematology	Hemoglobin, Platelets, White blood cells, Differential (Basophils, Eosinophils, Lymphocytes, Monocytes, Neutrophils, Other (absolute value preferred , %s are acceptable)
Chemistry	Albumin, Alkaline phosphatase, ALT , AST, Calcium, Magnesium, Phosphorus, Chloride, Sodium, Potassium, Creatinine, Creatine kinase, Direct Bilirubin, Total Bilirubin, Total Cholesterol, Triglycerides, Blood Urea Nitrogen (BUN) or Urea, Uric Acid, Amylase, Lipase, Glucose (fasting)
Urinalysis	Microscopic Panel: Red Blood Cells, White Blood Cells, Casts, Crystals, Bacteria, Epithelial cells
Coagulation	International normalized ratio [INR]), Activated partial thromboplastin time (APTT)
Hepatitis markers	HBV-DNA, HbsAg, HbsAb, HbcAb, HCV RNA-PCR (at baseline and as clinically indicated)

Test Category	Test Name
Pregnancy Test	A serum pregnancy test must be performed at screening (at the local laboratory) ≤ 14 days before first dose of study treatment, and at EOT. Subsequent tests may be urine tests (refer to 'Pregnancy and assessments of fertility' section).

8.4.2 Cardiac assessments

8.4.2.1 Electrocardiogram (ECG)

A standard 12 lead ECG (single or triplicate) will be performed according to the relevant Visit Evaluation Schedule ([Table 8-1](#)). Electrocardiograms (ECGs) must be recorded after 10 minutes rest in the supine position to ensure a stable baseline/according to the ECG investigator manual. The preferred sequence of cardiovascular data collection during study visits is ECG collection first, followed by vital signs, and blood sampling. Additional, unscheduled, ECGs may be performed at the discretion of the investigator at any time during the study as clinically indicated. Unscheduled ECGs with clinically significant findings should be collected in triplicate. The Fridericia QT correction formula (QTcF) should be used for clinical decisions.

Triplicate ECGs should be recorded approximately 2 minutes apart. The mean QTcF value should be calculated from each of the triplicate ECGs assessments. All ECGs need to be collected and copies kept in the medical record for central review, if requested by the sponsor.

Twelve (12)-lead ECGs will be obtained using an ECG machine that automatically calculates heart rate and measures PR, QRS, QT, and QTcF intervals. ECG data will be read and interpreted locally.

Any identifier details must be redacted e.g. participant initials, date of birth.

Clinically significant abnormalities must be recorded on the CRF as either medical history/current medical conditions or adverse events as appropriate.

Table 8-6 ECG collection plan

Week (or Cycle)	Day	Time	ECG Type	Number of ECG
Screening	-28 to -1	Anytime	12 Lead	3
3	1	Anytime	12 Lead	3
6	1	Anytime	12 Lead	3
Week 15 and every 9 weeks thereafter and at EoT	1	Anytime	12 Lead	3
Unscheduled (as clinically indicated)		Anytime	12 Lead	1 (3 if clinically significant)

Interpretation of the tracing must be made by a qualified physician and documented on the appropriate CRF. Each ECG tracing should be labeled with the study number, participant initials (where regulations permit), subject number, date, and kept in the source documents at the study site.

Clinically significant abnormalities present when the participant signed informed consent should be reported on the Medical History eCRF page. Clinically significant findings must be discussed with Novartis prior to enrolling the participant in the study. New or worsened

clinically significant findings occurring after informed consent must be recorded on the Adverse Events eCRF page.

8.4.2.2 Echocardiogram (ECHO)

Decreases of the LVEF have been observed in participants receiving trametinib. Therefore, ECHO or MUGA (ECHO is preferred) must be performed to assess cardiac ejection fraction in regular intervals according to the relevant schedule ([Table 8-1](#)).

The same procedure (ECHO or MUGA) should be performed at baseline and at follow-up visit(s). Dose modification guidance and stopping criteria for LVEF decrease are provided in [Table 6-13](#).

8.4.3 Pregnancy and assessments of fertility

Male participants

A condom is required for all sexually active male participants to prevent them from fathering a child AND to prevent delivery of study treatment via seminal fluid to their partner.

Male patients (including those that have had a vasectomy) taking the dabrafenib and trametinib combination therapy must use a condom during intercourse, and for 16 weeks after stopping treatment, and should not father a child during these periods.

In addition, male participants should not donate sperm for the time period specified above.

Women of child-bearing potential

All pre-menopausal women who are not surgically sterile will have pregnancy testing. Additional pregnancy testing might be performed if requested by local requirements.

Women of child-bearing potential, defined as all women physiologically capable of becoming pregnant, must use highly effective methods of contraception during dosing and for 16 weeks after stopping treatment with dabrafenib and trametinib combination therapy. Highly effective contraception methods include:

- a. Total abstinence (when this is in line with the preferred and usual lifestyle of the participant). Periodic abstinence (e.g., calendar, ovulation, symptothermal, post-ovulation methods) and withdrawal are not acceptable methods of contraception.
- b. Female sterilization (have had surgical bilateral oophorectomy with or without hysterectomy), total hysterectomy, or tubal ligation at least six weeks before taking study treatment. In case of oophorectomy alone, only when the reproductive status of the woman has been confirmed by follow up hormone level assessment.
- c. Sterilization (at least 6 months prior to screening) for male partners. The vasectomized male partner should be the sole partner for that participant.
- d. Placement of a hormonal or non-hormonal intrauterine device (IUD) or intrauterine system (IUS) with a documented failure rate of less than 1% per year.

Notes:

- a. Double-barrier contraception: condom and occlusive cap (diaphragm or cervical/vault caps) with a vaginal spermicidal agent (foam/gel/cream/suppository) are not considered highly effective methods of contraception.
- b. Hormonal-based methods (e.g. oral contraceptives) are not considered as highly effective methods of contraception due to potential drug-drug interactions with dabrafenib and/or trametinib
- c. Women are considered post-menopausal and not of child bearing potential if they have had 12 months of natural (spontaneous) amenorrhea with an appropriate clinical profile (i.e. age appropriate, history of vasomotor symptoms) or have had surgical bilateral oophorectomy (with or without hysterectomy), total hysterectomy, or tubal ligation at least six weeks ago. In the case of oophorectomy alone, only when the reproductive status of the woman has been confirmed by follow up hormone level assessment is she considered not of child bearing potential.

As per [Section 4.6](#), changes in safety assessments can be added as one of the risk mitigation procedure during public health emergency declared by local or regional authorities. If participants cannot visit the site to have serum pregnancy tests during a Public Health emergency as declared by Local or Regional authorities i.e., pandemic, epidemic or natural disaster, that limits or prevents on-site study visits, urine pregnancy test kits may be used. Relevant participants can perform the urine pregnancy test at home and report the result to the site. It is important that participants are instructed to perform the urine pregnancy test first and only if the test result is negative proceed with the administration of the study treatment. A communication process should be established with the participant so that the Site is informed and can verify the pregnancy test results (e.g., following country specific measures).

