- Clarified the inclusion criteria wording regarding BRAF central lab testing. Inclusion criteria 3: the term “fresh tumor tissue sample” changed to “new tumor tissue sample” (to align with [Section 8.5.3](#))
- Clarified the text of the Inclusion Criteria 4 for the use of platinum-based treatment as mandatory for pre-treated subjects (to align with Table 3-1)

[Section 6.5.2.10](#) Guideline dose modification and management for hemophagocytic lymphohistiocytosis (HLH)

- Added the guideline dose modification and management for hemophagocytic lymphohistiocytosis (HLH)

Section 6.6.2 Treatment of overdose

- Added new section on reference to treatment of overdose

Section 8.1 Screening

- Updated the rescreening procedure for screen failure subjects to enable the rescreening of all the subjects regardless of the initial screen failure reason (i.e CT /MRI results have expired (>28 days prior to enrollment) due to unexpected administrative issues or unexpected drug supply issue)
- Clarification that a new sample is not needed if participant already provided the tumor tissue samples for central testing of BRAF V600E mutation.

Section 8.1.2 Information to be collected on screening failures

- Added sentence to clarify that data and samples collected from participants prior to screen failures may still be analyzed

Section 8.3.1 Efficacy assessments

- Clarified the documentation of efficacy assessment in Central Imaging

Section 8.4.3 Pregnancy and assessments of fertility

- Updated the wording for women of child-bearing potential

Section 8.5.1 Clinical Outcome Assessments (COAs)

- Added text that eCOA assessments will not be reviewed by the Investigator/ study personnel.

Section 8.5.3 Biomarkers

- Updated description of the requirements for central BRAF V600 E mutation testing

Section 9.1.3 Withdrawal of informed consent/Opposition to use data/biological samples

- Removed text related to the withdrawal of consent in certain countries where consent is not required for the use of personal and coded data

Section 9.2 Study completion and post-study treatment

- Clarified the study completion date from 'approximately' 17 months to 17 months and separated from post-study treatment requirements

Section 10.1.4 Pregnancy Reporting

- Updated the Pregnancy reporting language

Section 10.1.5 Reporting of study treatment errors including misuse/abuse

- Clarified the reporting of study treatment errors including misuse/abuse

Section 12.5.2 Safety Endpoints

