 - Female sterilization (have had surgical bilateral oophorectomy with or without hysterectomy), total hysterectomy, or tubal ligation at least six weeks before taking study treatment. In case of oophorectomy alone, only when the reproductive status of the woman has been confirmed by follow up hormone level assessment.
 - Male sterilization (at least 6 months prior to screening). The vasectomized male partner should be the sole partner for that participant.
 - Placement of a non-hormonal intrauterine device (IUD) or intrauterine system (IUS) with documented failure rate of less than 1% per year.

Above measures for effective contraception must be applied for the following period of time: during dosing and for 16 weeks after stopping treatment with dabrafenib in combination with trametinib.

Note(s):

- Double-barrier contraception: condom and occlusive cap (diaphragm or cervical/vault caps) with a vaginal spermicidal agent (foam/gel/cream/suppository) are not considered highly effective methods of contraception
 - Hormonal-based methods (e.g., oral contraceptives) are not considered as highly effective methods of contraception due to potential drug-drug interactions with dabrafenib and/or trametinib
 - Women are considered post-menopausal and not of child bearing potential if they have had 12 months of natural (spontaneous) amenorrhea with an appropriate clinical profile (i.e. age appropriate, history of vasomotor symptoms) or have had surgical bilateral oophorectomy (with or without hysterectomy), total hysterectomy, or tubal ligation at least six weeks ago. In the case of oophorectomy alone, only when the reproductive status of the woman has been confirmed by follow up hormone level assessment is she considered not of child bearing potential.
15. Sexually active males (including those that have had a vasectomy) must use a condom during intercourse and should not father a child during this period. The amount of time a patient must use a condom after last treatment is as follows:
- 16 weeks post treatment discontinuation of dabrafenib in combination with trametinib
16. Participants with active Hepatitis B infection (HbsAg positive) will be excluded.

Note: Participants with antecedent of Hepatitis B (anti-HBC positive, HbsAg and HBV-DNA negative) are eligible.

17. Participants with positive test for hepatitis C ribonucleic acid (HCV RNA)

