6.2.1.1 Permitted concomitant therapy requiring caution and/or action

Dabrafenib

Effect of other drugs on dabrafenib

Based on in vitro studies, dabrafenib was shown to be primarily metabolized by CYP2C8 and CYP3A4. Medicinal products that are strong inhibitors or inducers of CYP2C8 or CYP3A4 are likely to increase or decrease, respectively, dabrafenib concentrations. Alternative agents should be considered during administration with dabrafenib when possible. Use caution if

strong inhibitors (e.g ketoconazole, nefazodone, clarithromycin, ritonavir, gemfibrozil) or inducers (e.g rifampin, phenytoin, carbamazepine, phenobarbital, St John's wort) of CYP2C8 or CYP3A4 are co-administered with dabrafenib.

Effect of dabrafenib on other drugs

Dabrafenib induces CYP3A4 and CYP2C9 mediated metabolism and may induce other enzymes including CYP2B6, CYP2C8, CYP2C19 and UDP glucuronosyltransferases (UGT). Dabrafenib may also induce transporters (e.g P-glycoprotein [P-gp]). Co-administration of dabrafenib and medicinal products which are affected by the induction of CYP3A4 or CYP2C9 such as hormonal contraceptives, warfarin or dexamethasone may result in decreased concentrations and loss of efficacy. If co-administration of these medications is necessary, monitor participants for loss of efficacy or consider substitutions of these medicinal products. Use caution if co-administration of CYP2C or CYP3A4 substrates with narrow therapeutic index is required. Refer to the Tafinlar label for further information.

Trametinib

Based on in vitro and in vivo data, trametinib is unlikely to significantly affect the pharmacokinetics of other medicinal products via interactions with CYP enzymes or transporters.

Dabrafenib and trametinib

Based on the mechanism of action of dabrafenib and trametinib, vaccines are not expected to have an interaction with these drugs, therefore are not prohibited. However, investigators should use their best clinical judgment on the use of live vaccines considering the potential immunocompromised state of cancer patients.

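### Protocol 8.4.3 item d lists a hormonal IUD/IUS as highly effective contraception, against note b of the same section and the governing exclusion 14; item d should be corrected (minor).

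*Protocol*

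**What the plan says.** Section 8.4.3 of the protocol requires that women of childbearing potential "must use highly effective methods of contraception during dosing and for 16 weeks after stopping treatment with dabrafenib and trametinib combination therapy". It then lists the methods that qualify. Item d of that list is "Placement of a hormonal or non-hormonal intrauterine device (IUD) or intrauterine system (IUS", subject to a documented failure rate below 1% per year. Note b, directly after the list, states: "Hormonal-based methods (e.g. oral contraceptives) are not considered as highly effective methods of contraception due to potential drug-drug interactions".

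Exclusion criterion 14 (Section 5.2) covers the same subject. Its intrauterine bullet reads "Placement of a non-hormonal intrauterine device (IUD) or intrauterine system (IUS) with documented failure rate of less than 1% per year", and its note says "Hormonal-based methods (e.g., oral contraceptives) are not considered as highly effective methods of contraception due to potential drug-drug interactions with dabrafenib and/or trametinib". It sets the same period: "Above measures for effective contraception must be applied for the following period of time: during dosing and for 16 weeks after stopping treatment".

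Two other places bear on which text prevails. Section 4.5 makes adherence to the contraception requirements in the exclusion criteria a condition of taking part, and says that someone whose compliance is in doubt should neither enter nor continue. The opening of Section 5 says that a deviation from any eligibility criterion keeps a patient out of the study.

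**The concern.** A hormonal intrauterine device satisfies item d. The same device is a hormonal-based method, which note b and the exclusion 14 note say is not highly effective. Site staff who look only at the list in 8.4.3 could accept a method that the eligibility criterion does not accept.

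The rule exists to prevent fetal exposure: Section 4.5 speaks of unknown risks to the fetus. What is at stake is participant safety and, for a woman accepted on the strength of item d alone, an eligibility deviation. Nothing in the estimation of response rate, PFS, duration of response or OS depends on it.

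**Working it through.** No formula applies to the main point. It rests on comparing current protocol text.

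**Step 1. Status of a hormonal IUD/IUS under each statement**

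| Place | What it says of a hormonal IUD/IUS |
|---|---|
| 8.4.3 item d | Highly effective (named expressly) |
| 8.4.3 note b | Not highly effective (hormonal-based method, no exemption) |
| Exclusion 14 note | Not highly effective (same statement as note b) |
| Exclusion 14 bullet | Names only the non-hormonal kind; its list is introduced as examples, so omission alone does not exclude |

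The two notes are one statement made twice, and the bullet is not exhaustive. The rows should therefore not be counted as three votes against one. The weight lies on the note, which is categorical, and on which section governs.

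**Step 2. Do the sections cover the same time?** Both say dosing plus 16 weeks: 16 × 7 = 112 days after the last dose. The conflict cannot be explained as one rule for entry and another for later.

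**Step 3. Which text governs?** Section 4.5 points to the exclusion criteria for the contraception requirements, both for entering and for continuing. Section 5 makes eligibility deviations exclusionary. Section 7 repeats the duty to follow the contraception requirements without naming a section. No passage names the 8.4.3 list as the controlling one. Exclusion 14 governs, so item d is the outlier.

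**Step 4. Who could be affected?**
- The documents do not give the number of women of childbearing potential.
- The Amendment 4 rationale records 34 participants enrolled and treated at its release (13-Mar-2023), against about 40 planned (Section 3): 40 − 34 = about 6 of either sex still to enter.
- Women already enrolled also count while on dosing or within 112 days of the last dose.
- The SAP's last update is dated 15-Oct-2024, before final database lock. From 13-Mar-2023 that is 582 days, about 19 months, so the trial is late in its course. The documents do not show whether anyone is still within the period.

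**Step 5. What already limits the risk?** Table 8-1 schedules urine pregnancy tests on Day 1, at Weeks 3, 6, 9 and 12, and every 3 weeks from Week 15. Table 8-5 adds serum tests at screening and end of treatment. Study treatment must stop on pregnancy (Sections 9.1.1 and 10.1.4). These measures detect pregnancy and do not prevent it, and Table 8-1 shows no test in the 16 weeks after end of treatment.

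**The case against.** **The notes may mean systemic hormones only.** Item d is specific to intrauterine methods, note b is general, and its only example is oral contraceptives. Within 8.4.3 alone, the specific could be read as an exception to the general. That reading is possible, but the protocol does not state it, and it does not remove the conflict with exclusion 14, whose note has no exception and whose bullet names only the non-hormonal device.

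**The matter may be too small to raise.** Much of this stands. Few women can be affected, exclusion 14 already gives the right answer, on-treatment testing is frequent, and no analysis changes. What remains is a safety instruction that is wrong as written and costs two words to correct.

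A reader might also infer more than the documents support:
- *That sites face two equal rules and the intended one is unknown.* Sections 4.5 and 5 point to exclusion 14.
- *That hormonal contraception is banned.* Section 6.2.1.1 warns that dabrafenib may reduce the efficacy of hormonal contraceptives, but its instruction is a caution: "If co-administration of these medications is necessary, monitor participants for loss of efficacy or consider substitutions of these medicinal products". The notes say only that such methods do not count as highly effective.
- *That Amendment 4 introduced the error.* Its log for 8.4.3 says only "Updated the wording for women of child-bearing potential" and does not show which words changed.
- *That a hormonal intrauterine system fails with these drugs, or that women were exposed.* The documents contain no evidence on either.

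**Conclusion.** The inconsistency is real and sits in current, operative text. Item d of Section 8.4.3 is wrong against note b and against exclusion 14, which the protocol makes the controlling requirement. It is a minor participant-safety correction. It applies to one contraceptive method, in women of childbearing potential who are on dosing or within 112 days of the last dose, and it has no effect on any endpoint, analysis set or SAP analysis.

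The existence of the mismatch is certain from the wording. That item d is the part to change rests on Sections 4.5 and 5. The small practical size rests on the enrollment figures, the late stage of the trial and the testing schedule; the number of women concerned is not given and cannot be derived.

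**What to change.** Delete the words *hormonal or* from Section 8.4.3 item d. It then agrees with note b and, apart from an article, with the exclusion 14 bullet. Repeating *non-hormonal* before *intrauterine system* in both places would remove any doubt that the adjective covers both devices.

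If the sponsor holds evidence in the Investigator's Brochures, which are not among the documents reviewed, that hormonal intrauterine systems are acceptable with this combination, the alternative is to state that exemption in all four places: the exclusion 14 bullet and note, and 8.4.3 item d and note b.

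The edit slightly narrows the choice of methods shown in 8.4.3. Under Section 14.1 a text change needs a written amendment with sponsor and IRB/IEC approval and, where required, health-authority approval, so it should go in with the next amendment made for other reasons. Until then, a short clarification to sites that exclusion 14 governs is enough. If no woman of childbearing potential is still on dosing or within 16 weeks of her last dose, a stand-alone amendment would change nothing for participants.
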